**7.6.9.1. Endpoint / Variables**

- The PROMIS physical function score for each visit will be calculated as the mean of the scores for the 12 physical function items recorded for that visit, as long as at least 6 of the 12 item scores are complete. The change from baseline at Week 32 will be calculated from the Week 32 assessment and the Week 0 assessment.
- The PROMIS sleep score for each visit will be calculated as the mean of the scores for the 2 sleep items recorded for that visit; if either of the items has a missing score, the PROMIS sleep score will be assigned as missing for that visit. The change from baseline at Week 32 will be calculated from the Week 32 assessment and the Week 0 assessment.

**7.6.9.2. Strategy for Intercurrent (Post-Randomization) Events**

The treatment effect to be estimated (estimand) will be the ‘treatment policy’ effect of initial randomised treatment. A treatment policy strategy will be used for the intercurrent events of a) discontinuation of study medication and b) receipt of alternative HES medications. Subjects with missing change from baseline PROMIS score at Week 32 will be included in the analysis with the largest (i.e. worst) value observed for any subject.

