
 
To investigate the efficacy of mepolizumab compared with placebo with respect to patient and clinician reported symptoms, health status, and disease impact.
 
	
 
Change from baseline in HES symptom severity based on HES Daily Symptoms (HES-DS) at Week 32
 
Change from baseline in the BFI total score at Week 32
 
Clinician- and subject-rated overall response to therapy score (RTS) at Week 32
 
Change from baseline in Subject-rated symptom severity (SSR) at Week 32
 
Change from baseline in Modified Memorial Symptom Assessment Scale-Short Form (MSAS-SF) responses at Week 32
 
Change from baseline in physical function (Patient Reported Outcome Measurement Information System [PROMIS] physical function items) at Week 32
 
Change from baseline in sleep (PROMIS sleep items) at Week 32
 

Objectives	Endpoints

 
To characterize the patient burden of HES.
 
	
 
SF-36 v2
 
Healthcare resource utilization (HCRU)
 
Work Productivity and Activity Impairment Index – General Health (WPAI-GH) v2
 
Steroid perception questionnaire
 

 
To investigate the pharmacokinetics (PK) of mepolizumab.
 
	
 
Plasma concentration of mepolizumab
 

 
To investigate the pharmacodynamics (PD) of mepolizumab.
 
	
 
Total IL-5
 
Blood eosinophil levels
 

Safety Objectives	Safety Endpoints

 
To evaluate the safety of mepolizumab compared with placebo in subjects with HES receiving standard of care treatment over a 32-week study treatment period.
 
	
 
Adverse events including local injection site reactions and systemic reactions (e.g., hypersensitivity)
 
Vital signs
 
12-lead ECG
 
Hematological and clinical laboratory tests
 
Immunogenicity (anti-drug antibody)
 

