**7.6.9.3. Statistical Analyses / Methods**

Summary statistics for PROMIS physical function and sleep score at each visit will be presented, including change from baseline values.

Endpoint

 
• Change from baseline in PROMIS physical function score at Week 32.
 
• Change from baseline in PROMIS sleep score at Week 32.
 

Model Specification

 
• Wilcoxon Rank Sum test stratified by median baseline score (baseline score ≤ median and baseline score > median), baseline OCS dose (0 ≤ 20mg/day and >20mg/day prednisone or
 

equivalent) and region.
Model Results Presentation

• Number analysed in each treatment group.

• Median change from baseline at Week 32 in each treatment group.

• p-value for difference between treatments from Wilcoxon Rank Sum test.

Subgroup Analyses

• No subgroup analyses will be performed on this endpoint.

Sensitivity and Supportive Statistical Analyses

• A repeated measures analysis including assessments at Week 4, 8, 16, 24 and 32. In this analysis missing data will be assumed to be missing at random and will not be imputed with the largest i.e. worst value. A mixed effects model will be fitted with the following specification:

• Time point, treatment and region included as fixed categorical effects.

• Baseline score and baseline OCS included as continuous fixed covariates.

• Interaction terms for baseline-by-timepoint and treatment-by-time point interaction.

• The Kenward and Roger method (DDFM = KR) for approximating the denominator degrees of freedom to correct for bias in the estimated variance-covariance matrix.

• REPEATED statement with TYPE=UN to specify an unstructured covariance structure for the R matrix.

• The OBSMARGIN option on the LSMEANS statement in order to compute the adjusted geometric means with weights proportional to the input data set.

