### 16.6.2. Change from Baseline Definitions

Definition	Reporting Details
Change from Baseline	= Post-Dose Visit Value – Baseline
% Change from Baseline	= 100 x [(Post-Dose Visit Value – Baseline) / Baseline]
Ratio to Baseline	= Visit Value / Baseline

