2.52.	ITT	EFF_T8	Analysis of Change from Baseline in MSAS-SF Total and Subscale Scores (Treatment Policy Estimand, Mixed Model Repeated Measures)	
Include by line: Total MSAS-SF Score, MSAS-SF Global Distress Index, MSAS-SF Physical Subscale Score, MSAS-SF Psychological Subscale Score.
 
Scale 0 = Not at all distressed or bothered/No symptoms to 4 = Very much distressed or bothered/Almost constant symptoms.
	SAC

Efficacy: Tables					
No.	Population	IDSL / Example Shell	Title	Programming Notes	Deliverable
PROMIS Physical Function and Sleep					
2.53.	ITT	EFF_T6	Summary of PROMIS Physical Function Score	Present Baseline (week 0) up Week 32. Column header "Visit" rather than "Analysis Time Point". Add footnote: "Scale 1 = Cannot do/unable to do to 5 = Not at all/Without any difficulty."	SAC
2.54.	ITT	EFF_T7	Analysis of Change from Baseline in PROMIS Physical Function Score at Week 32 (Treatment Policy Estimand)	Scale 1 = Cannot do/unable to do to 5 = Not at all/Without any difficulty.	SAC
2.55.	ITT	EFF_T8	Analysis of Change from Baseline in PROMIS Physical Function Score (Treatment Policy Estimand, Mixed Model Repeated Measures)	Scale 1 = Cannot do/unable to do to 5 = Not at all/Without any difficulty.	SAC
2.56.	ITT	EFF_T6	Summary of PROMIS Sleep Score	Present Baseline (week 0) up Week 32. Column header "Visit" rather than "Analysis Time Point". Add footnote: "Scale 1 = Not at all difficulty in falling asleep /Never trouble staying asleep to 5 = Very much difficulty in falling asleep /Always trouble staying asleep."	SAC
2.57.	ITT	EFF_T7	Analysis of Change from Baseline in PROMIS Sleep Score at Week 32 (Treatment Policy Estimand)	Scale 1 = Not at all difficulty in falling asleep /Never trouble staying asleep to 5 = Very much difficulty in falling asleep /Always trouble staying asleep.	SAC
2.58.	ITT	EFF_T8	Analysis of Change from Baseline in PROMIS Sleep Score (Treatment Policy Estimand, Mixed Model Repeated Measures)	Scale 1 = Not at all difficulty in falling asleep /Never trouble staying asleep to 5 = Very much difficulty in falling asleep /Always trouble staying asleep.	SAC

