2.22.	ITT	EFF_F5	Change from Baseline in MSAS-SF Total and Subscale Scores - Treatment Difference vs Placebo (Treatment Policy Estimand, Mixed Model Repeated Measures)	
Either one plot per page, 4 pages with by line, or 4 lines on one plot, as data permit: Total MSAS-SF Score, MSAS-SF Global Distress Index, MSAS-SF Physical Subscale Score, MSAS-SF Psychological Subscale Score.
 
Present adjusted mean treatment difference (95% CI) change from baseline by time (weeks) from repeated measures model – Week 0, 4, 8, 12, 16, 20, 24, 28, 32.
 
Add footnote: “Note: Adjusted for baseline (week 0) score and region. Scale: 0 = Not at all distressed or bothered/No symptoms to 4 = Very much distressed or bothered/Almost constant symptoms.”
	SAC

Efficacy: Figures					
No.	Population	IDSL / Example Shell	Title	Programming Notes	Deliverable
PROMIS Physical Function and Sleep					
2.23.	ITT	EFF_F4	Change from Baseline in PROMIS Physical Function and Sleep Score (Treatment Policy Estimand, Mixed Model Repeated Measures)	
One plot per page, 2 pages with by line: PROMIS Physical Function Score, PROMIS Sleep Score.
 
Present adjusted mean (95% CI) change from baseline by time (weeks) from repeated measures model – Week 0, 4, 8, 16, 24, 32.
 
Add footnote: “Note: 1. Adjusted for baseline (week 0) score and region. 2. Sleep score scale 1 = Not at all difficulty in falling asleep /Never trouble staying asleep to 5 = Very much difficulty in falling asleep /Always trouble staying asleep. 3. Physical function scale 0 = Not at all distressed or bothered/No symptoms to 4 = Very much distressed or bothered/Almost constant symptoms.”
	SAC

Efficacy: Figures					
No.	Population	IDSL / Example Shell	Title	Programming Notes	Deliverable

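### The worst-case rule for missing PROMIS change names the best case for physical function

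*SAP*

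**What the plan says.** SAP 7.6.9.2 covers PROMIS physical function and PROMIS sleep with a single imputation rule: "Subjects with missing change from baseline PROMIS score at Week 32 will be included in the analysis with the largest (i.e. worst) value observed". The imputed values feed the stratified Wilcoxon Rank Sum test in 7.6.9.3, reported in Table 2.54 for physical function and Table 2.57 for sleep. The supporting repeated measures analysis does not use them; there, "missing data will be assumed to be missing at random and will not be imputed with the largest i.e. worst value".

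Three other places fix the direction:

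- **Sign of change** (16.6.2): "Post-Dose Visit Value – Baseline".
- **Physical function scale** (16.10.5, Tables 2.53 to 2.55): "Scale 1 = Cannot do/unable to do to 5 = Not at all/Without any difficulty".
- **Sleep scale** (16.10.5, Tables 2.56 to 2.58): "Scale 1 = Not at all difficulty in falling asleep /Never trouble staying asleep to 5 = Very much difficulty in falling asleep".

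Section 7.6.9.1 derives the physical function score as the "mean of the scores for the 12 physical function items recorded for that visit", with no reversal of items. SAP 2.1 lists the endpoint as exploratory.

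**The concern.** The same parenthetical appears for HES-DS, BFI total, RTS, SSR and MSAS-SF (SAP 7.6.4.2 to 7.6.8.2). Higher is worse on all of those, so the largest change is indeed the worst. Physical function is the only score under this wording where higher is better. A programmer who codes the maximum gives every subject with a missing Week 32 change the best result seen in the trial; one who codes the worst case takes the minimum. The plan does not settle which, and the mock shells are not in the documents.

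At stake is the main Wilcoxon p-value for physical function, and the reported median if it is computed on imputed data. Missing values should be expected: the protocol's Time and Events table marks no PROMIS assessment in the column for subjects who stop study treatment early, nor at the early withdrawal visit.

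**Working it through.** **Direction.** Change = post-dose value − baseline. Both scores run from 1 to 5, so change lies between 1 − 5 = −4 and 5 − 1 = +4.

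| Score | High score means | Largest change | Smallest change | Rule consistent? |
|---|---|---|---|---|
| Sleep | more difficulty | worst | best | yes |
| Physical function | less difficulty | best | worst | no |

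One passage points the other way. The footnotes to Figures 2.23 and 2.24 read "Physical function scale 0 = Not at all distressed or bothered/No symptoms to 4 = Very much distressed", which would make a higher score worse. That wording matches the MSAS-SF scale note used elsewhere in the display list and does not describe function items, so the scale in Tables 2.53 to 2.55 is the credible one.

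**Size on the rank scale.** The plan states no figure to reproduce. Let *a* and *b* be the missing fractions on mepolizumab and placebo, and θ the probability that an observed mepolizumab change exceeds an observed placebo change. With ties counted as one half, and ignoring the tie with the subject who holds the extreme value, the probability that a mepolizumab change exceeds a placebo change is:

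- maximum imputed: (1 − a)(1 − b)θ + a(1 − b) + ab/2
- minimum imputed: (1 − a)(1 − b)θ + b(1 − a) + ab/2

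The gap between the rules is a(1 − b) − b(1 − a) = a − b, whatever the SD or effect. With no true effect (θ = 0.5) the maximum gives 0.5 + (a − b)/2. For 2 of 40 missing on mepolizumab and 6 of 40 on placebo this is 0.5 + (0.05 − 0.15)/2 = 0.45, and 0.55 with the minimum. A simulation with those fixed counts gave 0.451 and 0.549. With 2 missing in each arm it gave 0.500 and 0.501.

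**Size as power and error.** Inputs: 40 per arm (Protocol 9.2.1). Assumed, because the documents do not give them: change normally distributed with SD 0.7, true benefit 0.4, each subject missing independently of outcome. The test is an unstratified Wilcoxon at two-sided 5%, with 20,000 replicates. With no missing data, power is 69.5%.

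| Missing, mepolizumab / placebo | Power, maximum imputed | Power, minimum imputed |
|---|---|---|
| 10% / 10% | 51% | 51% |
| 5% / 10% | 40% | 71% |
| 10% / 5% | 71% | 40% |
| 5% / 15% | 22.5% | 80% |
| 15% / 5% | 80% | 22.5% |

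With no true effect (nominal 2.5% per side; 2.6% per side simulated with no missing data):

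| Missing, mepolizumab / placebo | Maximum imputed | Minimum imputed |
|---|---|---|
| 15% / 5% | 11.2% falsely favour mepolizumab | 11.4% falsely favour placebo |
| 5% / 15% | 11.6% falsely favour placebo | 11.1% falsely favour mepolizumab |

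The inflation is smaller when missing counts are fixed instead of random: with 2 and 6 missing, 8.2% falsely favoured placebo under the maximum and 7.8% falsely favoured mepolizumab under the minimum (3,000 replicates).

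A stratified check (van Elteren test with modified ridit scores, 12 assumed strata, 2,000 replicates) showed the same pattern: 57% power with no missing data, 40% under either rule at 10%/10%, 14% against 71% at 5%/15%, and 71% against 14% at 15%/5%.

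**The case against.** The best defence is that this is a wording slip whose intent is stated in the same clause. The plan says worst, says it again in 7.6.9.3, and prints the scale direction beside the affected table. Harm requires someone to code the maximum against that purpose, and nothing in the documents shows that this happened. This stands as far as it goes: the intent is clear. But the rule equates worst with largest, and the Figure 2.23 and 2.24 footnotes would reassure a programmer who checked the direction there.

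The consequence is also small. PROMIS is exploratory and outside the testing hierarchy in SAP 5.5. The adjusted treatment difference and its confidence interval come from the repeated measures model, which does not use the imputation. This is correct and limits the importance of the point.

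The simulated sizes rest on assumed inputs, and only the missingness rates are varied. The largest contrasts need a threefold imbalance, and balanced missingness gives no difference. Missingness is taken as unrelated to outcome, although the visit schedule suggests it would follow treatment discontinuation. The stratified check borrows a scoring option that the SAP specifies only for BFI item 3. All of this is fair. The power figures are illustrations; the direction, and the rank-scale gap of a − b, do not depend on the assumed SD or effect.

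Finally, imputing the minimum inflates error by about the same amount in the opposite direction. That is true, and it is a property of extreme-value imputation, which the plan chose for its other patient-reported scores as well.

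**Conclusion.** The concern holds. For physical function, SAP 7.6.9.2 contradicts itself, and no other section repairs it. Read literally, the rule reverses the plan's worst-case intent and favours the arm with more missing data. That is anti-conservative for mepolizumab if mepolizumab loses more subjects, and can hide a real benefit if placebo does; the documents do not indicate which is likelier.

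The two readings differ on the rank scale by the difference in missing fractions, for example 0.15 − 0.05 = 0.10. Under the stated assumptions that can move power between 22.5% and 80%. The exposure is one exploratory p-value and possibly one median. The primary and secondary endpoints, PROMIS sleep and the repeated measures analysis are unaffected. It should be fixed, because a planned result now depends on which of two conflicting words is programmed.

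**What to change.** In SAP 7.6.9.2, split the rule by score: for sleep, impute the largest observed change; for physical function, impute the smallest (most negative) observed change. Amend the matching parenthetical in 7.6.9.3, and say whether the reported median includes imputed values. The direction should be settled and documented before unblinding, so that it is not chosen with results in view.

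Two separate minor corrections belong in the same edit:

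- Replace the physical function footnote of Figures 2.23 and 2.24 with the 1 to 5 scale of Tables 2.53 to 2.55.
- Reconcile the item count, which is 12 in SAP 7.6.9.1 and 14 in Protocol 7.12.6. The completeness rule of at least 6 of 12 depends on it; half of 14 would be 7.

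The main change costs one sentence of SAP text and one line of code. It makes the analysis do what the plan says, penalising the arm with more missing data. Because the error inflation remains, the Wilcoxon result should be read alongside the repeated measures analysis.

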**7.6.9.3. Statistical Analyses / Methods**

Summary statistics for PROMIS physical function and sleep score at each visit will be presented, including change from baseline values.

Endpoint

 
• Change from baseline in PROMIS physical function score at Week 32.
 
• Change from baseline in PROMIS sleep score at Week 32.
 

Model Specification

 
• Wilcoxon Rank Sum test stratified by median baseline score (baseline score ≤ median and baseline score > median), baseline OCS dose (0 ≤ 20mg/day and >20mg/day prednisone or
 

equivalent) and region.
Model Results Presentation

• Number analysed in each treatment group.

• Median change from baseline at Week 32 in each treatment group.

• p-value for difference between treatments from Wilcoxon Rank Sum test.

Subgroup Analyses

• No subgroup analyses will be performed on this endpoint.

Sensitivity and Supportive Statistical Analyses

• A repeated measures analysis including assessments at Week 4, 8, 16, 24 and 32. In this analysis missing data will be assumed to be missing at random and will not be imputed with the largest i.e. worst value. A mixed effects model will be fitted with the following specification:

• Time point, treatment and region included as fixed categorical effects.

• Baseline score and baseline OCS included as continuous fixed covariates.

• Interaction terms for baseline-by-timepoint and treatment-by-time point interaction.

• The Kenward and Roger method (DDFM = KR) for approximating the denominator degrees of freedom to correct for bias in the estimated variance-covariance matrix.

• REPEATED statement with TYPE=UN to specify an unstructured covariance structure for the R matrix.

• The OBSMARGIN option on the LSMEANS statement in order to compute the adjusted geometric means with weights proportional to the input data set.

## 8. HEALTH OUTCOMES ANALYSIS

### 8.1. SF-36 v2

- Certified scoring of the SF-36 survey will be performed using OPTUM™ software.
- The eight domain scores (bodily pain, general health, mental health, physical functioning, role emotional, role physical, social functioning and vitality) as well as the physical and mental component summary scores provided by the software will be converted to SDTM and ADaM data sets by GSK Biostatistics.
- Domain and component summary scores will be summarised by visit, including change from baseline.
- Summaries will be performed on the ITT population.
- No statistical analysis of the SF-36 scores will be performed.

### 8.2. Healthcare Resource Utilization (HCRU)

- Healthcare resource utilisation associated with a HES flare will be summarised by treatment group.
- Summaries will be performed on the ITT population.
- For each resource type, the number of flares using resource, total amount of resource and mean (SD) resource per HES flare will be summarised.
- No statistical analysis of this endpoint will be performed.

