7.3.5. Healthcare Resource Utilization (HCRU)

All unscheduled HES-related healthcare utilization (Section 7.1) will be recorded in the CRF including telephone contacts, specialist nurse visits, visits to a physician's office, home visits (day and night time), outpatient visits, visits to urgent care, visits to the emergency department, and hospitalizations associated with the subject's worsening of symptoms. Hospitalization data should be categorized by ward type (e.g., intensive care unit [ICU] and usual care). Hospital length of stay in each type of ward will also be recorded.

The HCRU worksheet used by the subject to record all healthcare contacts experienced since the last visit will be presented to the investigator (or designee) at the clinic visits. Subjects will be asked to bring their worksheet to every study site visit as it will be used to assist subject recall in discussions with the investigator, for site staff to then enter as appropriate in the eCRF. The investigator (or designee) should ask the subject if any of the healthcare contacts that are recorded on the worksheet were due to a worsening of HES symptom. The investigator can refer to his/her records to verify or supplement information given by the subject, if necessary.

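### Healthcare use is collected for every HES worsening but displayed only when tied to a flare, and the only average is per flare; minor, on an exploratory descriptive endpoint

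*SAP*

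**What the plan says.** **Collection.** Protocol 7.3.5 states: "All unscheduled HES-related healthcare utilization (Section 7.1) will be recorded in the CRF including telephone contacts". The list goes on to "visits to urgent care, visits to the emergency department, and hospitalizations associated with the" subject's worsening of symptoms. The investigator asks whether the "healthcare contacts that are recorded on the worksheet were due to a worsening of HES symptom". The trigger is a worsening, not a flare. The schedule (Protocol 7.1; SAP 16.2.1) places healthcare resource utilisation (HCRU) at scheduled visits and not in the unscheduled flare column.

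**Analysis.** SAP 8.2 states: "Healthcare resource utilisation associated with a HES flare will be summarised by treatment group". For each resource type, "the number of flares using resource, total amount of resource and mean (SD) resource per HES flare will be summarised". The summaries use the ITT population, and "No statistical analysis of this endpoint will be performed". The only HCRU table (Table 3.3, SAP 16.10.7) and the only HCRU listing (Listing 27, SAP 16.10.16) are both titled as flare-associated use. No summary per subject or per unit of follow-up time is described.

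**Purpose.** HCRU sits under an exploratory objective, separate from the treatment-comparison objectives: to describe the burden that HES places on patients (Protocol 3; SAP 2.1).

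**The concern.** A flare is an event with a therapy threshold, so the collected data and the displayed data differ. A HES admission or emergency visit that led to no qualifying change in therapy enters the CRF and then appears in no HCRU table or listing. For an endpoint meant to describe patient burden, that is a gap in the description.

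The only average has the number of flares as its denominator. Flares occur after randomisation, and the trial expects them to be less frequent on mepolizumab. The per-flare mean therefore describes how a flare was managed in those who had one, and says nothing about flares that did not happen. At stake is the reading of one exploratory table. The primary result and the tested secondary endpoints are unaffected.

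**Working it through.** **1. Can a HES admission fall outside the flare definition?** SAP 7.1.1 and Protocol 7.3.1 give two routes. Route (a) is a documented clinical change needing either maintenance oral steroid raised by 10 mg/day or more for 5 days, or a cytotoxic or immunosuppressive drug added or increased. Route (b) is two or more courses of blinded active oral steroid. Admission alone meets neither.

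**2. Would the safety tables pick it up?** Not reliably. Protocol 12.4.1 excludes expected signs and symptoms of HES from adverse events unless they are worse than expected. Protocol 12.4.2 adds that something that is not an adverse event cannot be a serious one, and gives admission for the disease under study as an example. A sub-threshold HES admission could therefore be missing from both sets of displays.

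**3. The plan's own figure.** No figure is stated for HCRU. The flare proportions come from Protocol 9.2.1: 60% v 22%, 40 per arm, two-sided 5%, 90% power. With continuity correction:

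- difference: 0.60 − 0.22 − 1/40 = 0.355
- null SE: √(2 × 0.41 × 0.59 / 40) = 0.110
- alternative SE: √((0.24 + 0.1716) / 40) = 0.1014
- power: Φ((0.355 − 1.96 × 0.110) / 0.1014) = 91.5%

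Exact power with Fisher's test is 91.9%; without correction the formula gives 94.8%. The stated 90% is consistent with a corrected or exact test, so the two proportions can be used as they stand.

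**4. What each summary would show.** Assumptions not in the documents: one flare per flaring subject, the same use c per flare in both arms, and full 32-week follow-up.

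- Flares: 40 × 0.60 = 24 v 40 × 0.22 = 8.8.
- Mean per flare: 24c/24 = c v 8.8c/8.8 = c; ratio 1.00.
- Total amount: 24c v 8.8c; ratio 8.8/24 = 0.37. With c = 0.5 this is 12 v 4.4; with c = 2 it is 48 v 17.6.
- Per randomised subject: 0.60c v 0.22c, which is 63% lower (1 − 0.22/0.60).
- Per subject-year: 40 × 224/365.25 = 24.5 years per arm, giving 0.98c v 0.36c.

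Varying flares per flaring subject from 1 to 2 and c from 0.1 to 2 leaves the ratios unchanged.

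**5. If use per flare differs.** Suppose treatment mainly prevents milder flares, so that 25% of placebo flares and 50% of mepolizumab flares lead to admission (assumed). The per-flare mean is 0.25 v 0.50, apparently worse on mepolizumab, while admissions are 24 × 0.25 = 6.0 v 8.8 × 0.50 = 4.4.

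**6. Effect of leaving out non-flare use.** Take flare use of 12 v 4.4. Let a share q of all placebo use lie outside flares, and give mepolizumab the same non-flare amount, 12q/(1 − q) (assumed).

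| q | Non-flare use per arm | All use, placebo v mepolizumab | Ratio |
|---|---|---|---|
| 0.10 | 1.33 | 13.33 v 5.73 | 0.43 |
| 0.25 | 4.0 | 16.0 v 8.4 | 0.525 |
| 0.50 | 12.0 | 24.0 v 16.4 | 0.68 |

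The flare-only ratio is 0.37 in each row, so under this assumption the restriction makes the arms look further apart.

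**7. Follow-up time.** SAP 16.6.1 already derives total observed time. The schedule does not mark HCRU in the column for subjects who stop study treatment early, although those subjects stay in the study to Week 32. Observed time may therefore exceed the time during which HCRU was collected.

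**The case against.** The strongest reply is that this is a burden description and not a treatment comparison. It is exploratory and untested. Use per flare is a fair description of what a flare costs, and flare prevention is already tested in the primary endpoint and three secondary endpoints. A reader can combine the flare rate with use per flare. The totals by arm are planned, allocation is 1:1, and dividing by the number of subjects is trivial. The shell for Table 3.3 is not reproduced, so its layout cannot be checked. All of this stands, and it is why the point is minor. It does not answer the omission of non-flare use, which cannot be recovered from any planned HCRU display.

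Three stronger readings are tempting and are not supported:

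- A reader might infer that the endpoint as a whole could show no difference when treatment prevents flares. That is true of the per-flare mean only. The number of flares using a resource and the total amount are shown by arm and would fall with flares prevented.
- A reader might infer that dropping non-flare use hides a benefit. With similar non-flare use in both arms it does the opposite (step 6).
- A reader might infer that SAP 2.4 should have listed the restriction as a change from protocol. Protocol 9.4.5 leaves the details of exploratory analyses to the analysis plan and specifies no HCRU summary, so nothing stated there was changed.

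**Conclusion.** The point holds in a limited form. Protocol 7.3.5 collects all unscheduled HES-related use due to worsening, while SAP 8.2, Table 3.3 and Listing 27 show only the flare-associated part. The planned totals and flare counts would reflect flares prevented; the per-flare mean would not, and it could move in either direction if treatment changes the mix of flares.

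The size of the omission cannot be known from the documents, which do not say how many HES contacts fall below the flare threshold. The 10% to 50% range, equal non-flare use in both arms, one flare per flaring subject and equal use per flare are all assumptions. The ratio of 1.00 per flare follows directly from the last of these and illustrates what that statistic cannot see; it does not predict the result. This is a cheap improvement to a descriptive table and carries no consequence for the trial's main conclusions.

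**What to change.** In SAP 8.2, Table 3.3 and Listing 27, cover all recorded unscheduled HES-related use, by randomised arm in the ITT population. For each resource type:

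- give the number and percentage of subjects with any use, with subjects who had none kept in the denominator;
- give the number per subject-year;
- split both into flare-associated and non-flare use, and state the rule that links a contact to a flare, since SAP 8.2 gives none;
- keep the per-flare mean (SD) as secondary description.

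Base subject-years on the time during which HCRU was actually collected. Confirm from the CRF whether collection continued after early treatment discontinuation. Total observed time from SAP 16.6.1 is the right denominator only if it did.

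The cost is a change of SAP wording, one revised descriptive table and one revised listing, using data already in the CRF.
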